2.3 Tertiary Objectives (Exploratory)

- To determine if the study drug combination affects bone health
- To determine if the study drug combination affects comprehensive geriatric assessment domains
- To determine if the study drug combination affects quality of life

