¤ After disease progression, follow-up will occur every 6 months (+/- 2 months) for first year after disease progression and as clinically indicated thereafter. Each subsequent antineoplastic therapy and survival status are the only required data point following progression.

¤ Comprehensive geriatric assessment (CGA) will be performed at baseline, end of cycle 1 and every 24 weeks during the study protocol until week 61 and at the time of progression. FACT-P will be performed along with CGA

¤ DEXA scan must be obtained within 2 years prior to registration for all patients. Follow-up DEXA scans should be obtained after 2 years of protocol treatment for patients not receiving denosumab or bisphosphonates. DEXA scan is not indicated for those who are on treatment with bisphosphonates or denosumab.

¤ For patients without radiographic evidence of metastatic disease at enrollment of study protocol, disease assessment with radiographic studies are not necessary unless there is evidence of PSA progression (see Section 6.0) or clinically indicated. For patients with radiographic evidence of metastatic disease at enrollment of study protocol, disease assessment with radiographic studies should be performed as indicated in the above study calendar and may be performed more frequently if clinically indicated by the same methods used at baseline. Chest Imaging may include either chest X-ray or CT chest at the discretion of the treating physician. After week 97, for patients with stable PSA, scans to be performed at the time of progression or as clinically indicated

¤ Treatment will be given daily and will continue until disease progression or other reason for discontinuation of protocol treatment (see Section 7.4) Study drug will be dispensed every 12 +/- 4 weeks and a 120 day supply of medication will be provided at each visit.

¶ This procedure is not mandatory but should be discussed with all patients enrolled in the protocol and can also be considered during the treatment course to prevent further worsening of breast tenderness when considered appropriate..

¤ Followed until death, study closure, or withdrawal of consent.

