9.3 Tertiary (Exploratory) Efficacy assessments

9.3.1 Change in Bone Health

ADT is known to effect bone strength. Compared to men with prostate cancer who do not receive treatment with ADT, patients with prostate cancer treated with ADT have a 13-30% increased risk of osteoporotic fractures.(65) Loss of lean muscle mass coupled with declined strength from ADT predisposes to a high risk of falls, which in the setting of osteoporosis leads to increased fracture risk. To determine the impact of study treatments of bone health, we will assess changes in bone density by comparing results of DEXA scans prior to and at the end of study treatment. To accurately examine their impact on bone health, only patients who are on the study drugs for at least 1 year will be included for this analysis. Additionally, due to the bone strengthening effects of bisphosphonates and denosumab, patients who receive these therapies will be excluded from this secondary endpoint analysis.

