10.3 Tertiary Endpoints

10.3.1 Changes in BoneHealth

This will be expressed as a difference between the mean T scores on bone densitometry at baseline and at 2 years of follow-up (Section 8.0). A 95% confidence interval for the difference will be constructed using the standard approach for paired measurements [67]. We will also compute the frequency and the percentage of subjects with osteopenia (T score = -1.0 to -2.5) and osteoporosis (T score < - 2.5) at baseline and at 2 years of follow-up.

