13.0 REGISTRATION GUIDELINES

13.1 Registration Timing

Patient's enrollment must occur up to 28 days prior to the start of treatment with the study drug combination. All patients must have a signed informed consent prior to registration.

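### The baseline DEXA may be up to 2 years old, so the exploratory 2-year T-score change can include pre-treatment change that the analysis cannot separate out

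*Combined protocol and SAP*

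**What the plan says.** The DEXA footnote in Section 8.0 sets both scan times. For baseline: "DEXA scan must be obtained within 2 years prior to registration for all patients". For follow-up: "Follow-up DEXA scans should be obtained after 2 years of protocol treatment for patients not receiving denosumab or bisphosphonates".

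Section 10.3.1 analyses the "difference between the mean T scores on bone densitometry at baseline and at 2 years of follow-up" and adds: "A 95% confidence interval for the difference will be constructed using the standard approach for paired measurements". It also tabulates osteopenia and osteoporosis at the same two time points. It does not limit, adjust for or report the age of the baseline scan.

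The link to the drugs is made elsewhere. The tertiary objective in Section 2.3 is "To determine if the study drug combination affects bone health". Section 9.3.1 sets out to measure the impact of study treatment by "comparing results of DEXA scans prior to and at the end of study treatment", and says that "only patients who are on the study drugs for at least 1 year will be included for this analysis". Users of bisphosphonates or denosumab are excluded.

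A general footnote in Section 8.0 asks for pre-enrolment scans within 28 days of Day 1. The calendar lists DEXA under its imaging heading, but that footnote does not name DEXA.

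**The concern.** A before-and-after comparison in a single-arm trial depends on the baseline being taken close to the start of treatment. Here the baseline may be recent for one man and 2 years old for another. Any bone change between the scan and Day 1 goes into the estimate and, under Sections 2.3 and 9.3.1, would be read as an effect of the study drugs.

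Two features of the design add to this. The paired confidence interval reflects sampling variation only, so neither the interval nor a larger sample would reveal the problem. Section 5.2.2 also allows earlier ADT given with definitive local treatment, provided that it stopped more than six months before entry. Section 9.3.1 itself says that ADT affects bone. A man with an old baseline scan could therefore have been on ADT, or recovering from it, between that scan and Day 1.

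**Working it through.** The plan states no figure for the interval between scans, so there is none to reproduce. The check is date arithmetic followed by a simple model of the bias.

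**Inputs from the documents**
- Age of baseline scan at registration: 0 to 2 years (Section 8.0, DEXA footnote).
- Registration to first dose: up to 28 days, or 28/365.25 = 0.08 years (Section 13.1: "Patient's enrollment must occur up to 28 days prior to the start of treatment with the study drug combination").
- Day 1 to follow-up scan: nominally 2 years (Sections 8.0 and 10.3.1), with a visit window of plus or minus 4 weeks.
- Minimum exposure for inclusion: 1 year (Section 9.3.1).

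**Interval between scans** = (baseline scan to Day 1) + (Day 1 to follow-up scan)
- Shortest: about 0 + 2 = 2 years.
- Longest, nominal: 2 + 2 = 4 years, of which 2/4 = 50% is before treatment.
- Adding the 28-day lag gives 4.08 years (51% before treatment). Adding the 4-week window as well gives 4.15 years.
- If the follow-up scan is done at week 97 (96 weeks, 1.84 years), the longest is 2 + 0.08 + 1.84 = 3.92 years.
- If the 1-year minimum in Section 9.3.1 governs, the interval could be 2 + 1 = 3 years, with 2/3 = 67% before treatment.
- If the general 28-day scan footnote covered DEXA, the longest would be 2.08 years and the pre-treatment share at most 0.077/2.077 = 3.7%.

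**Effect on the estimate.** Let L be the years from baseline scan to Day 1, r0 the yearly T-score change before treatment and r1 the yearly change on treatment.

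Measured change = r0 × L + r1 × 2. Ratio to the on-treatment change = 1 + (r0/r1) × (L/2).

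The documents give no rates, so these are assumptions, with r0 = r1:

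| Yearly loss | True 2-year change | L = 1 year | L = 2 years |
|---|---|---|---|
| 0.02 | -0.04 | -0.06 | -0.08 |
| 0.05 | -0.10 | -0.15 | -0.20 |
| 0.10 | -0.20 | -0.30 | -0.40 |

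The ratio is 1.5 at L = 1 and 2.0 at L = 2. If L is spread evenly over 0 to 2 years, its mean is 1 and the mean ratio is 1.5.

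Without equal rates those figures do not hold. With no loss before treatment (r0 = 0) the ratio is 1. With recovery before treatment it is below 1. With loss before treatment and almost none on treatment it has no upper bound.

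**Does a per-year rate solve it?** Take r0 = 0, r1 = -0.10 and L = 2. The raw change is -0.20, which is the correct on-treatment change. Divided by the 4 years between scans it becomes -0.05 per year, half the true on-treatment rate.

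**How many men a restricted analysis would hold.** Section 10.1 uses 0.40 for 2-year PSA-PFS in its margin-of-error formula: 0.40 × 40 = 16 men. An exponential curve with the alternative median of 3.04 years gives 0.63 × 40, or about 25. If scan ages are spread evenly over 24 months (assumed), a quarter fall within 6 months: about 4 to 6 men, before removing users of bone-protecting drugs. In that set the pre-treatment share is at most 0.5/2.5 = 20%.

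**Earlier ADT.** It may fall between 24 and 6 months before entry, so up to 24 - 6 = 18 months of ADT could lie between the baseline scan and Day 1.

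**The case against.** The best defence is that the general 28-day scan footnote already covers DEXA. That is a possible reading, but the DEXA footnote is specific and its 2-year limit would serve no purpose if 28 days applied. Nothing in the documents says that the general rule overrides it. What stands is that the two footnotes need reconciling.

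A second defence is that the endpoint is exploratory, has no hypothesis test and bears on neither the sample size nor the primary result. That is correct and limits the weight of the point.

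Third, Section 10.3.1 describes a difference with a confidence interval and does not itself call it a treatment effect. Also correct: the attribution comes from Sections 2.3 and 9.3.1.

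A reader might go further and infer that the plan will overstate bone loss, perhaps doubling it. The documents do not support that. They give neither the scan ages nor any rate of pre-treatment change, and recovery before Day 1 is possible, because earlier ADT must have stopped and testosterone must be non-castrate at screening (Section 5.2.1). A reader might also infer that the regimen was chosen to spare bone. Section 1.3 gives efficacy and duration of response as the reason for adding the 5-AR inhibitor.

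**Conclusion.** The concern holds in a limited form. As written, the 2-year T-score change can rest on scans about 2 to about 4 years apart, with up to about half of the interval before any study drug. That follows directly from the footnotes. The analysis therefore cannot separate pre-treatment from on-treatment change, and the osteopenia and osteoporosis percentages share the same weakness.

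The bias itself is a risk of unknown size. It probably runs towards overstating loss if men were already losing bone, and it vanishes or reverses if they were stable or recovering. The factors of 1.5 and 2 rest on a constant rate, and the average also on evenly spread scan dates. They are illustrations, not estimates for this trial.

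**What to change.** 1. Capture the dates of both DEXA scans. No section says that they are recorded for analysis, although source imaging reports should hold them.
2. In Section 10.3.1, report the distribution of time from baseline scan to Day 1 and from Day 1 to the follow-up scan.
3. Keep the raw paired difference and add one sensitivity analysis that accounts for baseline-scan age. Either regress the T-score change on time from baseline scan to Day 1 and report the estimate at zero lag with its 95% interval, or restrict to men with a recent baseline scan, for example within 6 months of Day 1. The regression assumes that pre-treatment change is linear in time and that scan age is unrelated to on-treatment change; say so.
4. Do not make the annualised change the main estimate. It averages the two periods and dilutes on-treatment loss when the pre-treatment rate is lower.
5. Reconcile the DEXA footnote with the general 28-day scan footnote. Reconcile Section 9.3.1 (scan when treatment ends, at least 1 year on drug) with the 2-year time point in Section 10.3.1 and the calendar.

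The cost is analysis wording and two dates per man, with no extra scan or visit. The limitation is precision: the restricted set may hold only about 4 to 6 men and the regression will be imprecise, so both should be presented as descriptive.

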9.0 END POINT DEFINITIONS: EFFICACY ASSESSMENT

9.1 Primary Efficacy Assessment

The primary efficacy assessment will be PSA PFS, which is defined as the length of time that a given subject will be alive and free from PSA progression. All patients will be treated with the study drugs for a minimum of 12 weeks before assessment for disease progression unless the patient develops significant treatment-related toxicity or worsening symptoms due to rapid disease progression. PSA progression will be defined according to the consensus guidelines of the Prostate Cancer Clinical Trials Working Group 2. For patients with a PSA decline at week 13 compared to the baseline value at the time of enrollment, the PSA progression date will be defined as the first date (after week 13) when there is a $\geq 25\%$ increase **and** an absolute $\geq 2\text{ng/ml}$ increase in PSA compared to the PSA nadir. For patients with a PSA rise at week 13, the PSA progression date will be defined as the first date (before week 13) when there is a $\geq 25\%$ increase **and** an absolute increase of $\geq 2\text{ ng/ml}$ in PSA compared to the baseline value at the time of enrollment. A confirmatory PSA is required three or more weeks after the date of PSA progression and it should demonstrate persistent elevation.

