6.0 OVERALL STUDY DESIGN AND PLAN

This study is a phase 2 open label efficacy and safety clinical trial evaluating the combination of oral enzalutamide (160 mg/day) and a 5-ARI either dutasteride (0.5 mg/day) or finasteride (5mg/day)in patients with systemic PCa. The study will enroll patients at two sites: University of Rochester Medical Center and the clinical cancer

center at the Froedtert & Medical College of Wisconsin. Approximately 40 patients will be enrolled.

Patients will receive study treatment until disease progression is documented and confirmed as defined by 1) PSA rise **with or without** radiographic evidence of disease progression or 2) the occurrence of a skeletal-related event. The occurrence of an adverse event, where continued administration of study drug is deemed not in the patient's best interest by the investigator and/or the sponsor, will also result in the removal of the patient from therapy. All patients will be treated with the study drug for a minimum of 12 weeks before assessment for disease progression unless the patient develops significant treatment-related toxicity or worsening symptoms due to rapid disease progression.

The consensus guidelines of the Prostate Cancer Clinical Trials Working Group 2 have been taken into consideration for the determination of disease progression in the study.(62) Disease progression based on PSA is defined as an increase in the PSA that is $\geq 25\%$ **and** $\geq 2\text{ng/ml}$ above the nadir PSA value. A confirmatory PSA is required three or more weeks later and it should demonstrate persistent elevation. Patients should continue on study treatment until this confirmatory PSA testing is performed to document PSA progression. Radiographic disease progression is defined by Response Evaluation Criteria in Solid Tumors (RECIST 1.1) (Appendix B) for soft tissue disease or the appearance of two or more new bone lesions on bone scan.

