The following assessments will be performed during the course of the clinical trial as detailed in section 8.0: soft tissue and visceral disease on computed tomography (CT) scan or on magnetic resonance imaging (MRI), bone disease on radionuclide bone scans, skeletal related events, analgesics use, Comprehensive Geriatric Assessment, Functional Assessment of Cancer Therapy-Prostate (FACT-P) and PSA. Radiologic studies will be read on site. Each site will ideally designate the same radiologist who will evaluate the images for any one patient for the duration of the trial. Repeat imaging for assessment of radiographic progression is not required once radiographic progression is determined.

Patients without radiographic evidence of metastatic disease at the time of enrollment will obtain repeat imaging only at the time of documented PSA progression or as clinically indicated. For patients with radiographic evidence of metastatic disease at enrollment, disease assessment with radiographic studies should be performed as detailed in section 8.0 and may be performed more frequently if clinically indicated. Chest imaging may include either chest X-ray or CT chest at the discretion of the treating physician.

CGA will be used to capture baseline health status prior to treatment and repeated at pre-specified intervals to document toxicities related to treatment and to assess any changes in functional status from baseline. A geriatric oncologist or his/her designee at each respective institution will administer CGA.

Forty patients will be recruited and treated until disease progression or meeting any reason for removal from treatment (see section 7.4). The primary efficacy end-point for this trial is PSA progression-free survival (PFS), which is defined as the length of time that a given subject will be alive and free from PSA progression as defined above in section 6.0.

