7.4 Criteria for Removal from Protocol Treatment

- Disease progression as defined by 1) PSA rise **with or without** radiographic evidence of disease progression or 2) the occurrence of a skeletal-related event (see section 6.0)
- Unacceptable toxicity very likely related to studydrugs
- Off study treatment for ≥ 30 days
- Initiation of new systemic treatment for PCa
- The patient may withdraw from the study at any time for any reason
- Death
- Product not available
- Lost to follow-up
- Decision by sponsor

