9.2 Secondary Efficacy Assessments

9.2.1 Absolute PSA Response

Failure to achieve a PSA of $\leq 4\text{ ng/ml}$ after seven months of combined ADT has been shown to be a negative predictor for survival in the SWOG 9346 trial.(63) We will report the PSA nadir value after initiation of study drugs and measure the absolute and relative PSA declines from the baseline PSA at the time of study enrollment.

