9.2.2 Time to PSA Nadir

We will assess the time to PSA nadir, which is defined as the time to achieve the lowest PSA value after initiation of study drugs. The prognostic significance of the time to PSA nadir is yet to be defined but Choueiri et al. suggested that a faster time to reach a PSA nadir after the initiation of ADT was associated with shorter survival duration in men with hormonal naïve metastatic prostate cancer.(64)

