10.0 STATISTICAL CONSIDERATIONS

10.1 Primary End-Point

The primary efficacy end-point for this trial is PSA progression-free survival (PFS) defined as the length of time that a given subject will be alive and free from PSA progression. Median PSA-PFS and 1-year and 2-year PSA-PFS probabilities will be estimated using the Kaplan-Meier method, with 95% confidence intervals constructed based on Greenwood's variance estimator, which is the default approach in SAS 9.3. (66-68) Confidence intervals for the median are given by $\{t : \hat{S}(t) - 0.5\} \leq \chi^2_{\alpha/2} V[\hat{S}(t)]\}$, where t represents all time points satisfying the inequality, $\hat{S}(t)$ is the Kaplan-Meier

estimate of PSA-PFS, $\chi^2_{\alpha/2}$ is a chi-square score with one degree of freedom

corresponding to the chosen confidence level (for 95% confidence $\chi^2_{\alpha/2} = 3.84$), and

$V[\hat{S}(t)]$ is the Greenwood's variance estimator. [64] Confidence intervals for the 1-year and 2-year survival probabilities will be constructed as $\hat{S}(t) \pm z_{\alpha/2} V[\hat{S}(t)]^{1/2}$, where $z_{\alpha/2}$ is

the standard normal score. (67)

It should be noted that in the absence of loss to follow-up (i.e., if vital status and PSA-progression status are known for each subject at the end of the study), $\hat{S}(t)$ coincides

with the observed proportion of subjects alive and without PSA progression by time t and $V[\hat{S}(t)]$ coincides with the usual estimator of the variance of a sample proportion $V[\hat{S}(t)] = [\hat{S}(t)][1 - \hat{S}(t)]/n$, where n is the number of subjects in the study. [65]

Sample size justification: The median PSA-PFS times under null and alternatives hypothesis are assumed to be 1.44 and 3.04 years (the corresponding 1 year PSA-PFS rates are 50% and 72% respectively). Based on this assumption, the one sample log-rank test shows that a sample size of $n=36$ has 82% power (two-sided test with significance level 0.05) to reject the null hypothesis if the median survival time is at least 3.04 years. Taking into account of withdrawal or loss to follow-up (no more than 10% for the first year), we plan to recruit 40 patients in the study.

Expected margin of error (one-half of the confidence width) of the 95% confidence intervals for $S(t)$ can be approximated by $1.96 \sqrt{[\hat{S}(t)][1 - \hat{S}(t)]/n}$. For 1-year and 2-year PSA-PFS this gives $1.96 \sqrt{0.72 \times 0.28/40} = 0.15$, $\sqrt{0.40 \times 0.60/40}$

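### Sections 6.0 and 9.1 give different PSA-progression rules for the primary endpoint, and 9.1 read literally leaves some week-13 risers with no progression date

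*Combined protocol and SAP*

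**What the plan says.** - **Section 6.0** has one criterion for all men: a rise of at least 25% and at least 2 ng/ml "above the nadir PSA value. A confirmatory PSA is required three or more weeks later". It gives no explicit date. The same section ties the primary endpoint to this criterion: "alive and free from PSA progression as defined above in section 6.0".
- **Section 9.1** divides men by their week-13 PSA relative to baseline. Decliners are compared with nadir, and "the PSA progression date will be defined as the first date (after week 13) when there is a" qualifying rise. Risers are compared with baseline: "For patients with a PSA rise at week 13, the PSA progression date will be defined as the first date (before week 13" on which the same two thresholds are met. Confirmation three or more weeks later is again required.
- **Both sections** call for at least 12 weeks of treatment before progression is assessed, with exceptions for toxicity and rapid progression. Both also cite the same working-group guideline.
- **Section 10.1** restates the endpoint by name and does not say which rule applies.
- **Nadir** is described only for the secondary endpoints, as a value reached on treatment: "We will report the PSA nadir value after initiation of study drugs" (Section 9.2.1) and "the time to achieve the lowest PSA value after initiation of study drugs" (Section 9.2.2). Neither 6.0 nor the primary-endpoint text says whether baseline can be the nadir.
- **Section 7.4** removes men from treatment for "Disease progression as defined by 1) PSA rise" and refers back to 6.0.

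**The concern.** The two rules differ in reference value and in the dates they allow. Three gaps follow from the wording of 9.1:

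1. A week-13 riser can be dated only before week 13. If his first qualifying value comes at week 13 or later, 9.1 gives him no date.
2. A decliner can be dated only after week 13, so a qualifying rebound at week 13 itself does not count.
3. A man whose PSA equals baseline at week 13 belongs to neither branch.

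The risers' window also sits badly with the 12-week minimum in the same section. It can be read as back-dating: assess at week 13, then place the event at an earlier visit. That reading still gives no date to a riser who had no qualifying earlier value.

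The same PSA series can therefore yield a different event date, or no event, depending on which section the analyst follows. In a single-arm trial tested against a fixed null, that choice should not be open at analysis.

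**Working it through.** **Inputs.** The thresholds (at least 25% and at least 2 ng/ml), reference values and windows come from Sections 6.0 and 9.1. The 40 men and the 72% and 50% 1-year rates come from Section 10.1. The PSA series are invented for illustration.

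**Conventions.** Because 6.0 sets no date, its date is taken as the first visit that meets its criterion. Rises are assumed confirmed. One PSA visit before week 13 is assumed, because the calendar's week numbers are not legible in the text available.

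**Both rules applied** (ng/ml: baseline, early visit, week 13, then later visits)

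| Series | Section 6.0 | Section 9.1, literal |
|---|---|---|
| 10, 9, 14 | Week 13: 14/9 = +56%, +5 | Riser; 9 is below baseline: no date |
| 10, 10.5, 11, 20 | At 20: 20/10.5 = +90%, +9.5 | Riser; 10.5 is +5%, +0.5: no date |
| 10, 6, 11 | Week 13: 11/6 = +83%, +5 | Riser; 6 is below baseline: no date |
| 10, 9, 10, 13, 16 | At 13: 13/9 = +44%, +4 | Unchanged at week 13: no branch |
| 10, 4, 7, 9, 12 | Week 13: 7/4 = +75%, +3 | Decliner; at 9, the next visit: 9/4 = +125%, +5 |
| 10, 2, 0.5, 0.4, 1, 3 | At 3: +2.6 over 0.4 | At 3: same date |

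The first three rows are the gap. They do not change if baseline may serve as nadir (in the second row, 20/10 = +100%). The 12-week minimum does not touch them either, since each 6.0 date is at week 13 or later. The fifth row depends on PSA still being drawn after week 13, because 9.1 needs its own later confirmation. The last row is an ordinary deep responder, for whom the rules agree.

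**A series that goes the other way: 10, 13, 16.** Section 9.1 dates the early visit (13/10 = +30%, +3). Section 6.0 has three possible answers:

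- Baseline can be nadir and early values count: the early visit.
- Baseline can be nadir but the 12-week minimum excludes early values: week 13 (16/10 = +60%, +6).
- Nadir is the lowest on-treatment value, 13: no date in the values shown, because 16/13 = +23.1% is below 25%.

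**Deleting the before-week-13 restriction alone.** 10, 9, 14 is then dated at week 13 (14/10 = +40%, +4), and 10, 10.5, 11, 20 at the value of 20. But 10, 6, 11 stays undated, since 11/10 is only +10% and +1. The reference values still differ.

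**Size per man.** At 72%, 40 × 0.72 = 28.8 men are event-free at 1 year. Suppose one man who failed within the year is left undated:

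- Kept event-free: 29.8/40 = 74.5%, a shift of 1/40 = 2.5 points.
- Censored at week 13 with no earlier events: 28.8/39 = 73.8%. With three earlier events: (37/40) × (1 − 7.2/36) = 74.0%.
- At the null rate of 50%: 21/40 = 52.5%, or 20/39 = 51.3%.

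These figures assume no other censoring before 1 year. With 36 men the upper shift is 1/36 = 2.8 points.

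**Comparison with the plan's own precision.** Section 10.1 prints a margin of error of 0.15. Its formula gives 1.96 × √(0.72 × 0.28/40) = 0.139 at 1 year and 1.96 × √(0.40 × 0.60/40) = 0.152 at 2 years. The printed line is broken in the text available, so nothing is made of the difference. One man's shift is small beside either value.

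**The case against.** The best reply is that Section 6.0 already settles the matter: it says the primary endpoint uses its own definition, so a failure goes undated only if the analyst sets that sentence aside and applies one parenthesis of 9.1 literally. That sentence does favour 6.0. It does not remove a conflicting and more detailed rule from the section headed as the endpoint definitions, and 10.1 does not choose between them. The restriction may be a slip, but nothing in the documents corrects it. The guideline that both sections cite is not reproduced, so it cannot settle the conflict here.

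Other objections stand and limit the point:

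- Section 6.0 states a criterion and not a date, so every 6.0 date above rests on a convention.
- Section 8.0 allows 4 weeks either way on visits after week 1, so a week-13 draw may fall in weeks 9 to 17. If there is more than one PSA draw before week 13, fewer risers may go undated.
- Few men may be risers at week 13. The background reports a PSA response in all 21 men of the site's own series, a decline of at least 80% in 96% of patients in a 99-man trial, and a median decrease of 99.6% on enzalutamide alone. Those regimens and populations differ from this trial's.

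A reader might infer that 9.1 biases the trial towards success. The documents do not support that: the gap series favour the treatment, but 10, 13, 16 can go the other way. A reader might also infer a material rise in the false-positive rate. That would need an assumed share of undated failures, and the documents give no basis for one.

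**Conclusion.** The conflict is real and lies in the text. Section 6.0 uses one rise-from-nadir rule. Section 9.1 uses a week-13 split with a different reference value for risers and windows that leave out week 13 itself. Read literally, some week-13 risers who meet 6.0 have no date under 9.1.

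The practical effect is probably small. The number of men is unknown and may be zero, and ordinary responders get the same date under both rules. With complete follow-up each undated failure adds at most 2.5 points to 1-year PSA-PFS at n=40. If one to four men were affected, an assumed range only, the shift would be at most 2.5 to 10 points. The net direction across all men is not determined. The conclusion rests on a literal reading of 9.1 and on the dating convention used for 6.0. No figure in the sample-size calculation is disputed. This should be fixed because it concerns the primary endpoint and can be settled by wording.

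**What to change.** This concerns endpoint dating only. Before PSA-PFS is analysed, use one definition in Sections 6.0, 9.1 and 10.1. State whether baseline can be the nadir and how values before 12 weeks count.

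**Simplest route.** Replace the dating text in 9.1 with the 6.0 criterion, dated at the first qualifying value that is later confirmed. This follows what 6.0 already says about the endpoint. It costs wording only and uses PSA values already collected.

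**If the week-13 split is kept.**

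- Delete the before-week-13 restriction for risers.
- Make the week-13 value eligible in the decline branch.
- Assign an unchanged PSA to a branch.
- Bring the endpoint reference in 6.0 into line.

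This route has a cost that wording cannot remove. Men are taken off treatment under 6.0, and the Section 8.0 footnote on follow-up after progression requires only subsequent therapy and survival status. For a man such as 10, 6, 11, the later PSA values that 9.1 needs may never be observed.

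Because the 6.0 rule also governs removal from treatment (Sections 6.0 and 7.4), the sponsor must reconcile those passages with whichever endpoint definition is chosen. No treatment-stopping rule is proposed here.
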